11.3.3 Visual Field

Visual field examinations will be assessed by automated perimetry with either the Humphrey Field Analyzer (using a 24-2 full threshold or 24-2 [SITA] Standard program) or the Octopus Perimeter (using a G1 Dynamic or Normal strategy or 24-2 Dynamic or Normal strategy program) at Screening, Baseline, Week 24, Week 52, Month 18, and Month 24/Exit. The same machine type (Humphrey vs. Octopus) should be used throughout the entire study for a given patient. Visual field overall results will be recorded on the eCRF as normal or abnormal. Abnormal findings include enlargement of blind spot, superior arcuate scotoma, inferior arcuate scotoma, paracentral scotoma, nasal step, central scotoma, generalized depression, and temporal scotoma and other. An eye may exhibit multiple abnormalities. Number and percentage of any post-baseline abnormal findings compared with baseline normal findings on visual field will be summarized by eye and by visit regardless of the machine type.

In addition, mean deviation or mean defect (MD) and change from baseline recorded in decibels (dB) will be analyzed by visit and by machine type (Humphrey and Octopus respectively). If the machine type is different between baseline and post baseline visit, no change from baseline will be derived. For patients, whose visual fields were assessed by one machine type as recorded, but there is a missing machine type at a post-baseline visit, the missing machine type will be assumed as the same machine type and the mean deviation or mean defect assessments will be derived.

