1.1 Glaucoma and Treatment

Glaucoma is a family of diseases commonly characterized by progressive optic neuropathy with associated visual field defects and is the leading cause of irreversible blindness in the world. Glaucoma is classified by Becker-Shaffer into 3 broad types: developmental, angle-closure, and open-angle glaucoma (OAG) (Stamper et al, 2009). Open-angle glaucoma is further categorized into primary OAG (POAG, sometimes also referred to as chronic OAG) and secondary OAG (which includes pigmentary and pseudoexfoliation glaucoma), the former being the predominant form of OAG. Primary OAG is characterized as a multifactorial optic neuropathy with a characteristic acquired atrophy of the optic nerve and loss of ganglion cells and their axons, developing in the presence of open anterior chamber (AC) angles, and manifesting characteristic visual field abnormalities (American Academy of Ophthalmology, 2010a). Globally, over 60 million people are estimated to be affected by glaucoma (the majority of whom have OAG) and these numbers are expected to increase over time (Quigley and Broman, 2006; Varma et al, 2011; Cook and Foster, 2012). Approximately 10% of eyes with elevated intraocular pressure (IOP) will progress to OAG over the course of a decade (Quigley et al, 1994).

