4.3 Inclusion Criteria

The following are requirements for entry into the study:

1. Male or female, 18 years of age or older

2. Written informed consent and authorization for use and release of personal health information are obtained in accordance with the relevant country and local privacy requirements, where applicable (eg, Written Authorization for Use and Release of Health and Research Study Information [United States (US) sites] and written Data Protection consent [European Union (EU) sites])
3. Patient is willing to withhold his/her IOP treatments according to the study requirements, and in the opinion of the investigator, can do so without significant risk. Note: If patients cannot discontinue their currently prescribed therapy for up to 8 weeks to meet the Washout period for study entry, the investigator may switch the patient's medication to one that requires a shorter washout interval during the washout of the original medication (see Section 8.2 and Table 7)
4. Patient has the ability to understand and the willingness to follow study instructions and requirements and is likely to complete all required visits and procedures
5. In the investigator's opinion, patient's IOP is not adequately managed with topical medication for reasons other than medication efficacy (eg, due to intolerance or nonadherence)
6. Negative pregnancy test at Baseline for females of childbearing potential

Ocular Inclusion Criteria for Both Eyes:

7. In the investigator's opinion, both eyes can be treated adequately with topical prostamide, prostaglandin, or prostaglandin analog (eg, LUMIGAN, Xalatan, Travatan) eye drops as the sole therapy if medication was taken as directed
8. In the investigator's opinion, patient's IOP can be adequately managed with SLT monotherapy
9. In the investigator's opinion, patient is a suitable candidate for SLT
10. Diagnosis of either OAG (ie, primary OAG, pseudoexfoliation glaucoma, pigmentary glaucoma) or OHT in each eye, requiring bilateral IOP-lowering treatment. (Note: diagnosis does not have to be the same in both eyes)
11. Central endothelial cell density by specular microscopy confirmed as being qualified by Reading Center assessment prior to beginning Washout
12. The iridocorneal angle must be independently confirmed as being qualified by 2 ophthalmologists using the following criteria:
 - a. Shaffer Grade ≥ 3 on clinical gonioscopy of the inferior angle

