20. The anticipated wearing of contact lenses during the study that deviates from the following (contact lens wear is allowed during the study, but is to be temporarily discontinued before study visits, and before and after an Administration Day according to the following):
 - a. Use of soft lenses should be discontinued at least 3 days prior to Baseline, and use of rigid gas permeable or hard contact lenses should be discontinued at least 1 week prior to Baseline
 - b. Use of soft lenses should be discontinued at least 3 days and use of rigid gas permeable or hard contact lenses should be discontinued at least 1 week prior to a scheduled study visit or Administration Day visit
 - c. Use of contact lenses of any kind should be discontinued for 1 week following any Bimatoprost SR (or Sham) administration
21. Central corneal thickness of < 480 or > 620 micrometers
22. Anticipated need for any incisional or laser ocular surgery during the study
23. History of anatomically narrow angle resulting in evidence of angle changes or any history of closed angle glaucoma. Note: historically narrow angled patients whose angle has been opened by cataract surgery or peripheral iridotomy may be eligible for enrollment if they have no evidence of angle abnormalities.
24. History or evidence of a peripheral iridotomy/iridectomy in the inferior iris

25. Any history of trabeculectomy or other types of glaucoma surgery, including a glaucoma seton or aqueous bypass stents
26. Peripheral anterior synechiae (PAS) in the inferior iridocorneal angle on gonioscopic examination at Screening
27. Visual field loss that, in the opinion of the investigator, is functionally significant (eg, split fixation, field defect within the central 10 degrees that is visually significant or likely to cause central visual impairment upon progression) or shows evidence of progressive visual field loss within the year prior to baseline (Note: Two visual fields are required for qualification, 1 performed within the 10 months prior to or at Screening, and 1 performed at baseline or during the washout period using the protocol-required testing method [see Procedure Manual]. The same test methodology should be used for all historical and study-related examination for a given patient.)
28. Evidence of macular edema during screening or in patient's medical history

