11.3.7 Biomicroscopy and Dilated Ophthalmoscopy

Biomicroscopy will be performed in each eye by slit-lamp examination at Screening, Baseline, and post-baseline visits. Dilated ophthalmoscopy examination of the vitreous, macula, and retina periphery will be performed at the Screening, Baseline, Week 12, Week 24, Week 40, Week 52, Month 16, Month 20, Month 24/Exit visits.

All findings will be coded using the MedDRA dictionary.

The Number and percentage of patient eyes with findings at least 2-grade increase in severity from baseline, or a status change from absence at baseline to presence at follow-up visit for findings which is not associated with a severity grade, at 1 or more post-baseline visits, will be summarized by preferred term in descending order of incidence rate. For findings that are associated with a severity grade, at least 2-grade increase in severity from baseline is defined as a change from no finding to 2 and above, from 0.5 to 2 and above, or from 1 to 3 and above from baseline at any of the follow-up visits.

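### On its plain reading, the only categorical visual-field table cannot count a new defect in an eye whose field was already abnormal at baseline

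*SAP*

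**What the plan says.** SAP 11.3.3 grades the field at two levels. The first is a binary result for the whole field: "Visual field overall results will be recorded on the eCRF as normal or abnormal". The second is a list of eight named defects plus an entry for other findings, with the remark "An eye may exhibit multiple abnormalities".

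Two summaries follow. The categorical one reads: "Number and percentage of any post-baseline abnormal findings compared with baseline normal findings on visual field will be summarized by eye and by visit", and it is pooled over perimeter type. The continuous one says that "mean deviation or mean defect (MD) and change from baseline recorded in decibels (dB) will be analyzed by visit and by machine type". The section sets no threshold for MD worsening and has no shift table and no stated rule for a new defect in an eye that already has one.

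On who enters, Protocol 4.3 requires "Diagnosis of either OAG (ie, primary OAG, pseudoexfoliation glaucoma, pigmentary glaucoma) or OHT in each eye". Protocol 1.1 describes primary open-angle glaucoma as "manifesting characteristic visual field abnormalities". Exclusion 27 in Protocol 4.4 removes "Visual field loss that, in the opinion of the investigator, is functionally significant", and also field loss that progressed in the year before baseline.

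For biomicroscopy and dilated ophthalmoscopy, SAP 11.3.7 counts ungraded findings by "a status change from absence at baseline to presence at follow-up visit".

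**The concern.** A safety table should let each eye show deterioration from its own starting point. If the comparison needs a normal field at baseline, an eye that already has a defect has nothing to be compared with. Take an eye that enters with a nasal step and later shows a paracentral scotoma. It is abnormal before and abnormal after, and it produces no event.

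Acceptable safety is one of the protocol's two clinical hypotheses, and visual field is a named safety measure. If glaucomatous eyes with existing defects cannot contribute, the table describes field safety mainly in eyes that entered with normal fields. A reader comparing Bimatoprost SR eyes with SLT eyes would not see from the table that the others were left out.

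**Working it through.** The documents give no figure for the visual-field analysis, so there is nothing to reproduce. The check is mainly of the text, followed by an illustration of scale.

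**1. Can an eye with an abnormal field enter?** Yes. Open-angle glaucoma eyes are eligible (Protocol 4.3), field abnormality is part of the disease as the protocol describes it (1.1), and only functionally significant or recently progressive loss is excluded (4.4, criterion 27). Milder, stable defects remain eligible.

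**2. Does the categorical rule count a new defect in such an eye?** Two readings are possible.
- *Whole field.* Normal is defined only for the overall result. An eye without a normal baseline then falls outside the comparison. This is the plain reading.
- *Defect by defect.* The sentence speaks of findings, and the SAP uses that word for the named defects. A paracentral scotoma absent at baseline and present later would then count, whatever else the eye had.

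Where the SAP wants the second kind of rule it writes it out, as in 11.3.7. That favours the first reading here but does not settle it.

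**3. How are comparable measures handled?**

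| Measure | Rule for worsening | Needs a normal baseline? |
|---|---|---|
| Visual acuity (SAP 11.3.2) | line-change categories, largest decrease | no |
| Hyperemia (11.3.4) | increase of at least 2 grades | no |
| Endothelial cell density (11.3.5) | percent-loss thresholds, greatest decrease | no |
| Biomicroscopy, ophthalmoscopy (11.3.7) | increase of at least 2 grades, or absent to present | no |
| Cup/disc ratio (11.3.8) | increase of 0.2 or more | no |
| Visual field (11.3.3) | abnormal against normal | yes, on the plain reading |

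**4. What else covers these eyes?** MD change is analysed by visit and machine type. Protocol 7.3 summarises continuous variables by sample size, mean, standard deviation, median, minimum and maximum. One extreme loss would show as the extreme value, but the number of eyes that worsened would not.

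**5. Illustration of scale.** The planned 160 patients give 160 eyes per treatment (SAP 15.0). Let *b* be the share abnormal at baseline, *w* the share of those that gain a defect, and *L* their loss in dB. All three are assumptions.

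- Eyes uncounted per treatment = 160 × *b* × *w*
- Fall in mean MD = (eyes uncounted × *L*) / 160, signed as for mean deviation

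| *b* | *w* | *L* (dB) | Abnormal at baseline | Uncounted | Fall in mean MD (dB) |
|---|---|---|---|---|---|
| 20% | 5% | 3 | 32 | 1.6 | 0.03 |
| 40% | 10% | 5 | 64 | 6.4 | 0.20 |
| 60% | 10% | 5 | 96 | 9.6 | 0.30 |

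The split by machine type does not weaken this signal. In the middle row, two equal strata with the losses spread evenly give 3.2 × 5 / 80 = 0.20 dB in each. With all the losses in one stratum, that stratum shows 6.4 × 5 / 80 = 0.40 dB.

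**The case against.** The strongest reply is that the sentence is loosely drafted rather than wrong. It refers to findings, the SAP's word for individual defects, and the different wording in 11.3.7 need not signal a different rule. That stands in part. The defect-by-defect reading is possible, so the exclusion of these eyes cannot be stated as certain. It does not remove the need for a change, because a programmer could follow either reading and produce different tables.

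A reader might go further and infer that eyes with an abnormal baseline are left unmonitored, or covered only by an average that hides individual losses. The documents do not support this. The descriptive convention includes the minimum and maximum. Ocular adverse events are summarised by treated eye (SAP 11.1), and all assessments go into the listings (SAP 17.5). The clause in Protocol 9.1.1 that keeps expected disease progression out of adverse-event reporting concerns signs collected as efficacy variables, whereas visual field is a safety measure; on its terms it does not take field worsening out. What remains is narrower: none of these routes counts how many baseline-abnormal eyes worsened.

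It is also tempting to say that most eyes are affected, or that the eyes left out are those most likely to progress. No share is given, ocular hypertension eyes are eligible too, and criterion 27 removes recent progressors. Neither statement can be made from the documents.

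**Conclusion.** The point holds as a gap in a descriptive safety summary. On the plain reading of SAP 11.3.3, a new defect in an eye already abnormal at baseline is not counted, and no other planned summary supplies that count. On the alternative reading the eye would count, but the SAP does not say so.

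The size is unknown. The illustrated 1.6 to 9.6 eyes per treatment rests on assumed values of *b* and *w* and applies only under the plain reading. The MD shifts also depend on an assumed loss per eye. No test or decision rule uses this table, and the primary IOP analysis is unaffected. This is a cheap improvement worth making, not a flaw that threatens the trial's conclusions.

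**What to change.** Replace the categorical sentence in SAP 11.3.3 with:

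> For all eyes, the number and percentage with at least one named visual-field defect absent at that eye's baseline and present post-baseline will be summarized by treated eye and visit, regardless of machine type, overall and by baseline field status (normal/abnormal).

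This follows the absence-to-presence logic of SAP 11.3.7, removes the ambiguity whichever reading was intended, and makes every eye with a baseline field able to contribute.

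The cost is one sentence and one table built from the defect list already recorded on the eCRF; no new data are collected. The downside is noise: some new defects will be test variability. The paired SLT eye serves as comparator, and the split by baseline field status shows where the counts arise.

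The count will not register deepening of a defect already present. A tabulation of eyes by MD worsening, by machine type, could add that. It is optional and would need a threshold fixed in advance, which the documents do not supply.

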11.3.4 Macroscopic Conjunctival Hyperemia

Severity assessment of hyperemia of each eye is performed at all scheduled visits except on any of the study treatment administration days using the following severity scale: 0 (None), +0.5 (Trace), +1 (Mild), +2 (Moderate), +3 (Severe) or 'Not Evaluable'.

The frequency distribution for the severity grade at each scheduled visit will be summarized by eyes. In addition, patients who had at least 2-grade increase from baseline in severity (worsening, i.e. a change from 0 to 2 and above, from 0.5 to 2 and above, or from 1 to 3 and above) will also be summarized for each eye by visits and analysis cycle. If the severity grade during an analysis cycle decreases from baseline, it will be considered as ‘no increase’.

11.3.5 Specular Microscopy

Endothelial cell density average (cells/mm²) will be assessed using specular microscopy performed on the central cornea of each eye at Screening, Week 4, Week 12, Week 24, Week 40, Week 52, Month 16, Month 20, and Month 24/Exit. Baseline endothelial cell density (measured at Screening), raw values, and change from baseline as well as percent changes from baseline will be summarized descriptively by visit and analysis cycle for each eye.

The number and percentage of patients will be tabulated by various thresholds (including but not limited to endothelial cell count change; e.g. $\geq 10\%$ gain, $\geq 10\%$ loss, $\geq 15\%$ loss, etc.) for the percent change from baseline at each visit and at the last visit (i.e., last visit assessment). Overall summary during the entire study and within analysis cycle will be summarized based on the greatest decrease from baseline.

Kaplan-Meier Analysis for Time to ECL Event

To further investigate the endothelial cell loss (ECL), time to event analyses will be performed on the ECL event using Kaplan-Meier (KM) method with graphical displays. The ECL event is defined as post-baseline percent loss in central corneal endothelial cell density (CECD) meeting a specified threshold. The analyses of ECL events will be performed for threshold values of $\geq 15\%$ and $\geq 20\%$. For each threshold value, *First Observed ECL* and *First Confirmed ECL* are defined as following:

1. *First Observed ECL*: The first *observed* ECL meeting the threshold is considered the initial ECL event.
2. *First Confirmed ECL*:

The first *confirmed* ECL event is defined as the first of two ECLs meeting the same threshold at two consecutive visits (scheduled or unscheduled) with CECD assessment done on different days.

- ✓ For discontinued or completed patients, if the first ECL event meeting the threshold occurs at the patient’s final CECD assessment before discontinuing/exiting the study, the loss will be counted as a confirmed loss at that date.
- ✓ For analyses performed prior to the final database lock, if a patient is continuing in the study and the first ECL meeting the threshold occurs at the

most recent CECD assessment visit before data cutoff, the loss will NOT be counted as a confirmed loss.

The KM analyses will be performed for each of the first *confirmed* ECL and the first *observed* ECL. Compelling evidence of intra-eye variability of CECD has been observed in global, well-controlled, randomized, multicenter studies despite methodological measures in place to control for CECD variability. Therefore, the key analysis for Time to ECL Event will be based on the confirmed ECL values. For each analysis, Time (days) is calculated as follows:

- Time to the First *Confirmed* ECL event = (Date of the First *Confirmed* ECL event – Date of the First Study Treatment) + 1,
- Time to the First *Observed* ECL event = (Date of the First *Observed* ECL event – Date of the First Study Treatment) + 1,

where the Date of First Study Treatment is the first date of Bimatoprost SR 10 µg or SLT administration. For eyes that did not have any observed ECL events, time to the first ECL event will be right-censored at the last available CECD assessment date.

For each scheduled visit, the tabulation will display the number of eyes at risk, cumulative number of eyes with events, and the cumulative probability of event and the associated 95% confidence interval.

Exposure Adjusted Analysis for ECL Rate

Additionally, to take into account the differences in follow up time, an exposure-adjusted analysis for ECL rate over the entire study period will be performed by treatment for Bimatoprost SR 10 µg and SLT treated eyes. Exposure time will be calculated for each treated eye. For eyes that experienced an ECL event during the study, exposure time is the number of days from the first study treatment administration to the date when the first ECL event occurred. For eyes without an ECL event, exposure time is the number of days from the first study treatment administration to the last assessment for CECD. Exposure time in person-years is calculated as (exposure time in days)/365.25. Exposure adjusted ECL rate will be calculated per 100 person-years as:

- $100 \times (\text{number of eyes that experienced the ECL event}) / \text{total exposure time in person-years for the treatment group}$.

Listings for patients with $\geq 20\%$ CECD loss at any visit will be provided.

Coefficient of Variation Average (CV_{AVE}): Coefficient of variation average of raw data and changes from baseline will be summarized descriptively by visit and analysis cycle for each eye.

Pleomorphism Average (HEX_{AVE}): Pleomorphism average of raw data and their changes from baseline will be summarized descriptively by visit and analysis cycle for each eye.

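### The confirmed endothelial-cell-loss rule (SAP 11.3.5) counts an unpaired final-visit loss only when no earlier loss reached that threshold, so an eye with more recorded losses can drop from event to non-event, with no censoring time defined

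*SAP*

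**What the plan says.** All of this is in SAP 11.3.5, Specular Microscopy.

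- **What an ECL event is.** "The ECL event is defined as post-baseline percent loss in central corneal endothelial cell density (CECD) meeting a specified threshold". One reading at the threshold is enough. The thresholds are 15% and 20%, and the definitions of first observed and first confirmed loss are applied "For each threshold value".
- **First observed.** The first observed "ECL meeting the threshold is considered the initial ECL event".
- **First confirmed, main rule.** The confirmed "ECL event is defined as the first of two ECLs meeting the same threshold at two consecutive visits (scheduled or unscheduled"), with the two assessments on different days.
- **First confirmed, final-assessment allowance.** The condition is written as "For discontinued or completed patients, if the first ECL event meeting the threshold occurs at the" last reading of the eye. When it is met, that single loss is taken as confirmed on the day of the reading, without a second one. A companion clause withholds this allowance from patients still in the study at an earlier database lock.
- **Status.** Because cell density varies within an eye, "the key analysis for Time to ECL Event will be based on the confirmed ECL values". SAP 12.3 repeats the time-to-ECL analyses separately for the fixed and flexible regimens.
- **Censoring.** One sentence serves both the observed and the confirmed analysis: "For eyes that did not have any observed ECL events, time to the first ECL event will be right-censored" at the last available assessment.

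**The concern.** The allowance exists because a loss at the last assessment cannot be followed by a second one. That reason holds equally for an eye with an isolated loss earlier in follow-up, but the word 'first' shuts that eye out. A sound event rule should never turn an event into a non-event when a further loss is added to the record. This one does.

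The censoring sentence leaves a second gap. In the confirmed analysis, an eye with an observed but unconfirmed loss has neither an event time nor a censoring time. This covers every eye with an isolated mid-study loss, whether or not there is also a loss at the end.

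At stake is the reproducibility and coherence of the curve that the SAP calls key for time to ECL, and of its repeats by regimen. Two programmers could score the same eyes differently.

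**Working it through.** The SAP states no ECL rate, so there is no figure to reproduce. The check has two parts.

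**1. The rule itself (no assumptions about rates).** Take a completed patient with the 8 scheduled post-baseline assessments in SAP 11.3.5 (Weeks 4, 12, 24, 40, 52; Months 16, 20, 24) and one threshold. Each assessment is loss or no loss, giving 2^8 = 256 patterns.

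- Patterns with no two adjacent losses: 55. Patterns with an adjacent pair: 256 − 55 = 201. These are events under any version of the rule.
- Patterns with a final-visit loss and no adjacent pair: 21. Month 20 must then be clear, so any earlier losses lie among the first six visits. With k non-adjacent earlier losses there are C(7−k, k) patterns: k = 0 gives 1, k = 1 gives 6, k = 2 gives 10, k = 3 gives 4.
- Rule as written: only the k = 0 pattern is added, 201 + 1 = 202 events.
- If any final-visit loss counted: 201 + 21 = 222 events.
- Difference: 20 patterns. All have the same final loss as the one pattern that is counted, plus 1 to 3 earlier losses.
- Patterns with no defined time in the confirmed analysis: 256 − 202 − 1 (the pattern with no loss) = 53. Even if all final-visit losses counted, 256 − 222 − 1 = 33 would remain.

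Three examples at the 15% threshold:

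| Losses at | Number of losses | Confirmed event as written? |
|---|---|---|
| Month 24 only | 1 | Yes, at Month 24 |
| Week 24, Month 24 | 2 | No |
| Week 12, Week 40, Month 16, Month 24 | 4 | No |

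These are counts of patterns, not probabilities. They show that the rule is inconsistent, not how often this occurs.

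**2. How many eyes (every input assumed).** The documents give neither cell-density variability nor a loss rate. Simulated model: percent loss at a visit = slope × time + baseline error + visit error. The slope is normal with mean 3% a year and between-eye SD 3%, set to zero if negative. Both errors have SD 4% of baseline.

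| Quantity | 15% threshold | 20% threshold |
|---|---|---|
| Confirmed, rule as written | 12.7% of eyes | 4.2% |
| Confirmed, any final-visit loss counted | 14.5% | 4.6% |
| Difference | 1.8 points | 0.4 point |
| Eyes out of 160 | about 2.8 | about 0.6 |

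The figure of 160 is the planned number treated with 10 µg (SAP 15.0), used here only as a scale. With measurement SD 3% or 5%, the 15% difference becomes about 0.8 or 2.8 points. With mean loss 1% or 6% a year (SD 4%), it becomes about 0.8 or 3.7 points.

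In the same base setting, 6.7% of eyes have a true Month 24 loss of at least 15%, and the strict two-consecutive-visit rule also counts about 6.7%.

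**The case against.** **'First' may mean the first of a pair that can no longer be completed.** The allowance sits directly under the confirmed definition, which speaks of the first of two losses. On that reading the omitted eyes would count. The reading is possible, but the SAP has just defined an ECL event as any single threshold loss and the initial event as the first one observed, and the allowance uses those words. At best the text is ambiguous. The censoring gap remains on either reading.

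**The earlier loss was contradicted by later readings, so it may be evidence of noise.** This has force. In the base setting only about 24% of the omitted eyes have a true loss of 15% or more. But among the eyes that the rule does count on a single final loss, the share is about 21%. Across the settings tried, the omitted eyes were about as likely as the counted ones to have a true loss, or more so. Noise is not a ground for treating the two groups differently.

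**A reader might infer that the rule understates corneal loss.** The documents do not support that. In the base setting the rule as written already gives 12.7% against a true 6.7%, and counting the omitted eyes moves it further away, to 14.5%.

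**A reader might also infer that it hides more loss in the worse treatment.** That holds only in absolute counts. At mean loss 1, 3 and 6% a year, the share of unpaired final losses discarded stays near 22–24%, while the relative shortfall in the confirmed rate falls from about 13% to 12% to 10%. Nothing in the documents shows a distorted comparison.

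**The losses are visible elsewhere.** They appear in the first-observed Kaplan-Meier analysis, the by-visit and last-visit threshold tables and, at 20% or more, the listing. The confirmed analysis is descriptive, with no test or decision rule. All of this stands and limits the consequence.

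**Conclusion.** The point holds as an inconsistency and an omission in the definition. Read with the SAP's own terms, the allowance makes confirmed status depend on the absence of earlier loss at that threshold. Eyes with an observed but unconfirmed loss are left without a time in the confirmed analysis. 'First' works per threshold, so an earlier 16% loss does not disqualify a first 20% loss at the end. An earlier loss at the assessment just before the last one is confirmed by the main rule.

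The likely size is small: about 2 percentage points of eyes at 15% (about 3 of 160) and well under 1 point at 20%, resting wholly on the assumed inputs above. The point does not establish that true loss is understated or that the treatment comparison is biased. It should be corrected because the analysis is the one named as key for time to ECL and the repair is cheap.

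**What to change.** Replace the allowance with: *For discontinued or completed patients with no earlier confirmed ECL, an ECL meeting the threshold at the final CECD assessment is counted as confirmed at that date, whether or not an earlier unconfirmed ECL occurred.*

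Add to the censoring rule: *In the confirmed analysis, eyes with no confirmed ECL are right-censored at the last available CECD assessment.*

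Report the strict two-consecutive-visit count next to the confirmed count, so that the reader can see how much rests on single final-visit losses.

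The cost is two sentences of SAP text, a small programming change and one extra row per table. The confirmed rate becomes slightly less favourable and takes in a few more noise-driven events, which is why the strict count belongs beside it.
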